2. SYNOPSIS

Trial Title	Fully hybrid 18F-PSMA PET/MRI as one-stop approach for the diagnosis of clinically significant prostate cancer	
Protocol Acronym/Number	RF-2021-12372278	
Protocol Version and Date	v2.0, 30 GEN 2023	
EudraCT number	NA	
Sponsor	IRCCS Ospedale San Raffaele [name]	
Funding Source(s)	Italian Ministry of Health	
Principal Investigator	[name], U.O. of Nuclear Medicine	
Trial Description	
This project aims to evaluate the role of fully hybrid PET/MRI with 18F-PSMA and multiparametric MR imaging (mpMRI) as one-stop approach for the diagnosis of clinically significant prostate cancer (csPCa).
 
Our main hypothesis is that adding 18F-PSMA PET to mpMRI prior to biopsy, will reduce the number of false negative findings, while at the same time, allowing also to reduce the number of unnecessary prostate biopsies in patients with low-risk, clinically indolent PCa.
	
	Primary	Secondary
Objectives	To assess the accuracy and the predictive value of fully hybrid 18F-PSMA PET/MRI for the diagnosis of csPCa	
 1) To compare the proportion of csPCa missed by 18F-PSMA PET scan or mpMRI alone 2) To report the reduction in the detection of clinically insignificant PCa when combining mpMRI and 18F-PSMA PET, and consequently the proportion of unnecessary biopsies potentially spared.
Endpoints	Diagnostic accuracy measured with sensitivity, specificity, positive and negative predicted value	
 1) The number of csPCa missed by PET and MR imaging when read independently 2) Only in patients with positive mpMRI and negative 18F-PSMA PET: The proportion of clinically insignificant PCa
Time point(s)	day 0: 18F-PSMA PET/MRI day 90 (+/- 90): prostate biopsy	
Phase	Phase II	
Trial Design	Monocentric, single-arm, prospective	

Trial Population	Men with clinical suspicion of csPCa.
Inclusion Criteria	1) Men at least 18 years of age referred with clinical suspicion of prostate cancer candidate for prostate biopsy 2) Feasibility to undergo all procedures listed in protocol 3) Ability to provide written informed consent
Exclusion Criteria	1) Prior diagnosis of prostate cancer 2) Contraindication to MRI (e.g. claustrophobia, pacemaker, estimated GFR lower or equal to 50mls/min) 3) Contraindication to prostate biopsy
Intervention(s)	
IMP(s)	18F-PSMA, 4 MBq/Kg, intravenous administration
NIMP(s)	Not applicable.

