4. BACKGROUND AND RATIONALE

Prostate cancer (PCa) is the second most common cancer in men, with 1,414,259 new cases in 2020, accounting for 15.1% of all cancer diagnoses within the male population (1). The current EAU Guidelines for PCa recommend performing mpMRI before prostate biopsy in men with clinical suspicion of PCa (2). However, the accuracy of mpMRI in detecting csPCa remains suboptimal and a significant proportion of unnecessary biopsies are performed in men with suspicious lesions on mpMRI (3). Several efforts were made to identify new diagnostic strategies to implement mpMRI performances. The use of PSMA PET, widely implemented for clinical management of PCa both in recurrent and primary setting, has recently gained interest for diagnostic purposes. In 296 men with suspicion of PCa, the combined use of ⁶⁸Ga-PSMA PET and mpMRI for PCa diagnosis showed improved sensitivity and negative predicted value for csPCa (4). Based on these results, the combination of mpMRI and ⁶⁸Ga-PSMA PET might reduce the number of prostate biopsies required to diagnose csPCa. In this prior study, mpMRI and ⁶⁸Ga-PSMA PET have been acquired and interpreted separately, with the risk of introducing potential confounders. Moreover, imaging-guided targeted biopsies were not systematically performed.

In this project, the role of hybrid PET/MRI with ¹⁸F-PSMA will be evaluated in PCa diagnosis. The major advantages of this innovative technology are the simultaneous acquisition of PET and mpMR imaging by using a fully hybrid PET/MRI scan and the use of ¹⁸F-PSMA with improved spatial resolution compared to ⁶⁸Ga-PSMA, due to its lower positron energy.

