6. OBJECTIVES AND ENDPOINTS

Objectives	Endpoints	Time point(s)
Primary Objective To assess the accuracy and the predictive value of fully hybrid ^{18}F -PSMA PET/MRI for the diagnosis of csPCa	Primary Endpoint Diagnostic accuracies of ^{18}F -PSMA PET and mpMRI will be calculated by means of sensitivity: true positive/(true positive + false negative) and specificity: true negative/(false positive + true negative) using the prostate biopsy result as reference standard.	PET/MRI examination at day 0, and biopsy at day 1-30 (within a month from imaging study)
Secondary Objectives To compare the proportion of csPCa missed by ^{18}F -PSMA PET scan or mpMRI alone	Secondary Endpoints The proportion of csPCa (defined by analysis of prostate biopsy cores, ISUP grade equal or higher than 2) missed by PSMA PET scan or mpMRI alone will be calculated.	PET/MRI examination at day 0, and biopsy at day 1-30 (within a month from imaging study)
Exploratory Objectives To assess the proportion of unnecessary biopsies potentially spared	Other Number of clinically insignificant PCa (ISUP grade 1) identified combining mpMRI and ^{18}F -PSMA PET.	PET/MRI examination at day 0, and biopsy at day 90 (+/-90)

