8. TRIAL DESIGN

In this single-arm phase II, prospective, monocentric study we will test whether addition of 18F-PSMA PET scan to mpMRI helps improving the diagnostic pathway efficiency in identifying those men who should necessarily undergo TBx, because of high-risk to harbor csPCa.

Furthermore, the combined use of 18F-PSMA PET and mpMRI for the diagnosis of PCa may also result in a reduced number of follow-up procedures in those patients who can safely avoid a prostate biopsy given the very low risk of harboring csPCa using a single, one-stop approach with both imaging modalities. A more efficient pre-biopsy triage test using the fully hybrid 18F-PSMA PET/MRI might result in the reduction of the total number of biopsies for men with a clinical suspicion of PCa, reducing also patient discomfort combining two different diagnostic procedures in one single step and avoiding, whenever possible, the biopsy-related side effects.

A total of 167 consecutive patients with a clinical suspicion of csPCa (defined as the presence of PCa with ISUP grade equal or higher to 2), referred to simultaneous 18F-PSMA PET/MRI with mpMRI, will be identified and enrolled. PET/MRI images will be qualitatively and quantitatively evaluated by an experienced Nuclear Medicine and an experienced Radiologist physicians. In particular, for qualitative evaluation, lesions classified as PI-RADS higher or equal to 3 on mpMRI images and/or showing pathologically increased 18F-PSMA uptake on PET images, will be considered as positive for csPCa. All men will then receive a prostate biopsy (12-core random systematic prostate biopsy plus eventual targeted biopsy) as back-up histology according to the results of PET/MR imaging.

Specifically, patients with both positive mpMRI and 18F-PSMA PET, defined as the presence of one or more lesions with PI-RADS higher or equal to 3 and an increased uptake of 18F-PSMA, will receive a 12-core random systematic prostate biopsy (TRUS-Bx) in addition to MRI targeted biopsy (MRI-TBx) and 18F-PSMA PET targeted biopsy (PSMA PETTBx).

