16. STATISTICS

16.1. Description of Statistical Methods

Diagnostic accuracies of 18F-PSMA PET and mpMRI will be calculated by means of sensitivity: true positive/(true positive + false negative); specificity: true negative/(false positive + true negative); PPV: true positive/(true positive + false positive); and NPV: true negative/(true negative + false negative) using the prostate biopsy result as reference standard.

- The assessment of quantitative imaging parameters, including radiomic features and conventional parameters, characterizing regions of csPCa will be performed by generalized Linear Mixed Models for binary responses. Logistic regression will be used for evaluating PET and MRI parameters and texture features in predicting the presence of csPCa, as defined by biopsy results. To assess the diagnostic performance of PET and MRI parameters, ROC curve analysis will be performed to select optimal cut-offs in predicting the presence of csPCa, as defined by cytological examination, and the corresponding diagnostic accuracy values will be computed.
- McNemar test will be used to compare the proportion of csPCa missed by 18F-PSMA PET or mpMRI alone (12).
- All statistical analyses and data processing will be performed using the R statistical package or the SPSS software. All p-value will be rounded to three decimal places. Statistical significance will be declared if the rounded p-value will be less than 0.050. Two-sided 95% confidence intervals will be calculated.

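### The main hypothesis is what adding PET to mpMRI changes, but no paired difference between the combination and mpMRI alone is pre-specified

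*Combined protocol and SAP*

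**What the plan says.** The synopsis gives the main hypothesis as "adding 18F-PSMA PET to mpMRI prior to biopsy, will reduce the number of false negative findings, while at the same time" reducing unnecessary biopsies in men with indolent disease. Section 8 repeats the aim: "we will test whether addition of 18F-PSMA PET scan to mpMRI helps improving the diagnostic pathway efficiency". Section 4 motivates the trial with an earlier 68Ga-PSMA study in which the combination "showed improved sensitivity and negative predicted value for csPCa".

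Section 16.1 lists sensitivity, specificity, PPV and NPV for PET and mpMRI, without saying whether the reads are combined or separate. Section 6 words the primary endpoint in the same way. The only comparison between imaging tests is: "McNemar test will be used to compare the proportion of csPCa missed by 18F-PSMA PET or mpMRI alone".

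On positivity, section 8 counts as positive for csPCa (ISUP grade 2 or higher) "lesions classified as PI-RADS higher or equal to 3 on mpMRI images and/or showing pathologically increased 18F-PSMA uptake on PET images", and section 10.6 repeats this. Section 8 also sorts patients into four imaging groups, but only to assign the type of biopsy.

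On spared biopsies, the synopsis has as secondary objective 2 "To report the reduction in the detection of clinically insignificant PCa when combining mpMRI and 18F-PSMA PET". Its endpoint, like the matching analysis in section 8, is the proportion of insignificant cancer among mpMRI-positive, PET-negative men. Section 6 lists the aim as exploratory and words the endpoint as "Number of clinically insignificant PCa (ISUP grade 1) identified combining mpMRI and" 18F-PSMA PET, with no subset. Section 8 also refers to "those patients who can safely avoid a prostate biopsy given the very low risk of harboring csPCa".

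**The concern.** An add-on hypothesis is a claim about the combination relative to mpMRI. Comparing PET alone with mpMRI alone asks which single test misses more csPCa, which is a different question. The two answers can diverge: two tests with equal sensitivity that find different cancers show no difference head to head, yet together find more than either. The comparison also uses only men with csPCa, so no between-test comparison is named in men without it, where the cost in false positives arises.

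The two halves of the hypothesis also need different strategies. If either test being positive makes the patient positive, the combination can only add positives to mpMRI. It may cut false negatives, but it cannot flag fewer men or fewer ISUP 1 cancers. The spared-biopsy analysis instead treats mpMRI-positive, PET-negative men as spared. It then counts ISUP 1 cancers in them without setting beside these the csPCa that sparing would miss, although the protocol speaks of avoiding biopsy safely.

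At stake is whether the trial reports, from data it will hold, a planned answer to its own main question with gain and cost side by side.

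**Working it through.** **The plan's own figure.** Section 16.2 assumes prevalence 56%, sensitivity 96% and precision ±4% at 95% confidence. csPCa men needed: 1.96² × 0.96 × 0.04 / 0.04² = 92.2, rounded up to 93. Total: 93 / 0.56 = 166.07, rounded up to 167. The stated 167 reproduces. It is sized for one sensitivity, not for a difference.

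**Expected counts.** 167 × 0.56 = 93.5 men with csPCa (94 used below) and 167 − 94 = 73 without.

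**Notation, csPCa men.** b = seen by PET only; c = seen by mpMRI only. Change in sensitivity from mpMRI alone:
- either test positive: +b/94
- both tests positive: −c/94
- PET alone decides: (b − c)/94

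McNemar tests b = c. It therefore addresses the add-on effect only if PET alone decides. Under either-positive all changes go one way, so the gain is the single proportion b/94 and its exact (Clopper-Pearson) interval applies.

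**Assumed cells.** The documents give no mpMRI sensitivity and no discordance, so b and c are assumptions. Four men are missed by both tests, which takes the 96% as the either-positive value; section 16.2 does not say which test it means.

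| both / PET only / mpMRI only / neither | exact McNemar p | either-positive gain (95% CI) |
|---|---|---|
| 80 / 5 / 5 / 4 | 1.0 | 5/94 = 5.3 points (1.7 to 12.0) |
| 70 / 10 / 10 / 4 | 1.0 | 10/94 = 10.6 points (5.2 to 18.7) |
| 60 / 15 / 15 / 4 | 1.0 | 15/94 = 16.0 points (9.2 to 25.0) |

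Now hold b at 10, so that mpMRI sensitivity is 80/94 = 85.1% and the gain is 10.6 points throughout. For c = 0, 2, 5, 10, 20 and 25, McNemar p = 0.002, 0.039, 0.302, 1.0, 0.099 and 0.017. In the last two mpMRI is ahead of PET. The p-value moves across its whole range while the gain stays fixed.

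**Upper bound under the other reading.** If the 96% refers to mpMRI alone, mpMRI misses about 4 of 94. Then b is at most 4, and the gain at most 4/94 = 4.3 points.

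**Cost side, either-positive.** With k PET-only positives among the 73 men without csPCa, specificity falls by k/73. For k = 5, 10 and 15 (assumed) the loss is 6.8, 13.7 and 20.5 points (exact 95% CIs 2.3 to 15.3, 6.8 to 23.8 and 12.0 to 31.6). No such comparison is named.

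**Spared-biopsy side.** The csPCa missed by sparing mpMRI-positive, PET-negative men is c. With c = 10 that is 10/94 = 10.6% of all csPCa. The planned endpoint for that subset counts only ISUP 1.

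**The case against.** The case on the other side is substantial.

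- The primary objective is not comparative: it is the accuracy of PET/MRI in a single-arm study sized for one sensitivity. McNemar is matched to secondary objective 1, and nothing offers it as the test of the add-on hypothesis. This stands. However, the synopsis calls the add-on effect the main hypothesis and section 8 says it will be tested, and section 16 contains no analysis of it against mpMRI.
- Much is recoverable. Under either-positive, subtracting csPCa missed by the combination from csPCa missed by mpMRI gives the gain (14 − 4 = 10 in the second row of the table). The csPCa count in mpMRI-positive, PET-negative men is a cell of the McNemar table, and that subset is itself a partial look at the add-on effect. This also stands. What is absent is pre-specification and a report of gain against loss.
- A reader might infer that the combined result is wholly undefined, and that the 70 / 10 / 10 / 4 table could yield a primary sensitivity of 95.7% (either-positive), 85.1% (PET decides) or 74.5% (both-positive). The documents do not support that. Section 8 defines patient-level positivity for each modality, and the and/or lesion rule makes either-positive the natural reading. No passage proposes the other two rules for the primary endpoint, and 85.1% is simply PET alone. The spared-biopsy analysis is a separate hypothetical strategy and does not redefine the primary index test.

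**Conclusion.** The point holds in limited form and should be fixed. The plan states an add-on hypothesis, names only a head-to-head comparison of the single tests in csPCa men, leaves the implied either-positive rule unstated per patient, and reports the spared-biopsy subset without the csPCa missed in it.

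The size depends on discordance that the documents do not give. With the assumed cells, a McNemar p of 1.0 is compatible with a gain of 5.3 or 10.6 points. If the planned 96% belongs to mpMRI, the gain is at most about 4.3 points. These are illustrations, not forecasts.

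A reader might also infer that McNemar is the wrong test or that 167 is miscalculated. Neither follows: the test suits secondary objective 1, and the sample size reproduces for its stated purpose.

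One further ambiguity bears on the remedy. Section 5.1 says PET results are evaluated jointly with mpMRI, while sections 8 and 10.6 have the readers blinded to each other. A composite of blinded reads need not equal a joint read.

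**What to change.** In section 16.1:

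1. State the implied either-positive rule per patient for the primary endpoint. Say whether it is built from the mutually blinded reads (sections 8 and 10.6) or from a joint read (section 5.1), and reconcile those passages. Align the spared-biopsy objective and endpoint across the synopsis, section 6 and section 8.
2. Pre-specify paired differences from mpMRI alone in sensitivity (csPCa men) and specificity (men without csPCa), with 95% CIs. Under either-positive each direction is fixed by construction, so the two must be read together. Do the same for the strategy implied by the spared-biopsy analysis, as a separate hypothetical analysis, stating how mpMRI-negative, PET-positive men are classed in it.
3. In mpMRI-positive, PET-negative men, report csPCa (ISUP grade 2 or higher) and benign counts beside ISUP 1.
4. Keep McNemar for secondary objective 1, and do not read it as evidence for or against the combination.

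The cost is wording and a few 2x2 tables. Biopsy in all men and separate blinded reads already supply the data; if a joint read is intended, it must be recorded as its own result. The downside is imprecision: for a gain of 10/94 the 95% CI is 18.7 − 5.2 = 13.5 points wide. These are analysis definitions only; no biopsy rule for patients is proposed.

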Biopsy protocol: Each patient will receive a 12-core random systematic biopsy (TRUSBx) and mpMRI targeted biopsy as standard clinical procedure. MpMRI software assisted targeted biopsy will be performed using the BioJet™ fusion system (D&K Technologies, Barum, Germany) (8,9). Before biopsy both the prostate and each mpMRI suspicious lesion will be contoured and superimposed with the transrectal (TR) ultrasound image. TR ultrasound will be performed using a Flex Focus 500 machine with a biplanar transducer (BK Medical, Herlev, Denmark) (10). In

addition, 18F-PSMA PET targeted biopsy will be also performed, using the BioJet™ fusion system relying on PET images co-registered with mpMRI images for a correct contouring of both prostate and 18F-PSMA PET ROIs and superimposition with ultrasound images. Each mpMRI and 18F-PSMA PET ROI will be biopsied with a 4-cores targeted biopsy. Prostate biopsies will be carried out using a 18-gauge needle and a biopsy gun providing a specimen size of 18-22 mm.

PET/MR quantitative analysis: ROIs on primary tumour showing 18F-PSMA uptake will be semi-automatically defined on transaxial PET images and the following semi-quantitative parameters will be extracted: maximum standardised uptake value (SUV_{max}), mean SUV (SUV_{mean}, using different thresholds and metabolic tumour volume (MTV) calculated at different thresholds. ROIs on the MR images, ADC and DCE maps will be drawn to measure MR parameters related to the lesions detected by MRI.

Radiomic analysis: Volumes of interest (VOIs) will be manually segmented on 18F-PSMA PET, T2w-images and ADC maps by expert Nuclear Medicine and Radiologist physicians in correspondence of the intra-prostatic findings referable to the site of primary tumour. IBSI compliant radiomic features (11) will be extracted from VOIs and features reduction and selection procedures will be used to define a smaller set of radiomic features showing the best discrimination between csPCa and clinically insignificant PCa or healthy tissue.

Remaining radio-pharmaceutical will be stored in a bunker at Ospedale San Raffaele and after radioactivity decay will be destroyed in accordance with the hospital and the applicable local, federal and national regulations.

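### Section 16.1 applies one unadjusted 0.050 rule to all quantitative and radiomic tests, so chance features could be declared significant predictors of csPCa

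*Combined protocol and SAP*

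**What the plan says.** Section 16.1 plans generalized linear mixed models for the quantitative imaging parameters that characterise regions of csPCa. It adds: "Logistic regression will be used for evaluating PET and MRI parameters and texture features in predicting the presence of csPCa". For the PET and MRI parameters, "ROC curve analysis will be performed to select optimal cut-offs in predicting the presence of csPCa". A McNemar test compares the proportions of csPCa missed by PET and by mpMRI. The section's last bullet covers all analyses: "All p-value will be rounded to three decimal places", then "Statistical significance will be declared if the rounded p-value will be less than 0.050", and finally "Two-sided 95% confidence intervals will be calculated".

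Section 10.6 shows how many parameters may enter. The conventional PET set is SUVmax, plus SUVmean "using different thresholds and metabolic tumour volume (MTV) calculated at different thresholds". MR parameters are measured on the MR images and on the ADC and DCE maps. For radiomics, "Volumes of interest (VOIs) will be manually segmented on 18F-PSMA PET, T2w-images and ADC maps", and IBSI-compliant features are extracted from those volumes. A reduction and selection step then keeps a smaller radiomic set that best separates csPCa from insignificant cancer or healthy tissue.

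Neither section gives the number of parameters, the number of thresholds, the selection method, a family of tests or an adjustment.

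**The concern.** The rule in 16.1 makes no distinction between the one test tied to a listed objective (McNemar) and a screen of many imaging parameters. A parameter with no relation to csPCa has about a 5% chance of passing it. As the number of such parameters grows, so does the number that pass by chance, and the plan as written would call each of them statistically significant. Section 22 foresees publication in the radiomics field, so these declarations would be read outside the trial. At stake is the credibility of individual imaging predictors. This is separate from how well the accuracy of a chosen cut-off is validated.

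**Working it through.** **Inputs from the documents.** The significance level is 0.050, applied after rounding to three decimals, with two-sided 95% intervals (16.1). There are three radiomic image sources, and SUVmean and MTV are repeated over an unstated number of thresholds (10.6). Prevalence is 56%, sensitivity 96%, precision 4% and N=167 (16.2).

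**Input that is missing.** The number of tests, k, is not given. The values of k below are assumptions.

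**Step 1: the plan's own figure.** Number of csPCa cases needed = 1.96² × 0.96 × 0.04 / 0.04² = 92.2, rounded up to 93. Then 93 / 0.56 = 166.07, rounded up to 167. The stated sample size is reproduced. It rests on the precision of sensitivity and on no p-value, so nothing below changes it.

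**Step 2: expected false positives.** With k parameters unrelated to csPCa, the expected number with p < 0.05 is 0.05 × k. If the tests are independent, the chance of at least one is 1 − 0.95^k.

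| k (assumed, all null) | Expected false positives | Chance of at least one, if independent |
|---|---|---|
| 5 | 0.25 | 22.6% |
| 10 | 0.5 | 40.1% |
| 20 | 1.0 | 64.2% |
| 50 | 2.5 | 92.3% |
| 100 | 5.0 | 99.4% |
| 300 | 15 | above 99% |

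Correlation between features changes the last column but not the expected count. The average reaches one at 20 null parameters (1 / 0.05).

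**Step 3: does the selection step solve this?** It may reduce the number of radiomic features tested. It is described only for radiomic features, so the conventional parameters repeated over thresholds are not covered. Its criterion is discrimination of csPCa, which is also the outcome of the later tests, and no separate data set or resampling is described. If features are chosen for their association with csPCa and then tested for it in the same patients, the resulting p-values are too small.

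**Step 4: rounding (minor).** A p-value from 0.0495 up to, but not including, 0.0500 becomes 0.050 and fails the rule. The effective threshold is therefore 0.0495 (z = 1.9643 instead of 1.9600). A 95% interval obtained by inverting the same test would exclude the null in that window. The window has probability 0.0005 under the null and about 0.0012 for a test with 80% power. It can occur: without continuity correction, a McNemar split of 15 v 6 gives (15 − 6)² / 21 = 3.857, p = 0.0495, and 18 v 8 gives (18 − 8)² / 26 = 3.846, p = 0.0499.

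**The case against.** The strongest reply is that this analysis is peripheral. Quantitative and radiomic parameters appear in none of the objectives or endpoints in the synopsis or section 6. Section 8 introduces them as an additional investigation of a potential role. The primary endpoint is estimated with no named test, and the McNemar comparison is a single test. This stands, and it limits the weight of the point. It does not remove it, because 16.1 gives these tests the same formal declaration of significance as McNemar and nowhere labels them exploratory.

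A second reply is that the count is unknown. Section 10.6 plans feature reduction, and 16.1 names models without saying that each feature gets its own test; a multivariable model on a reduced set also fits the text. This stands too. With 5 to 10 null features tested, and ignoring any bias from prior selection, only 0.25 to 0.5 false positives would be expected. Nor are all parameters likely to be null in a trial built on the premise that PSMA uptake and mpMRI findings track csPCa. A reader might infer that the trial is certain to report false predictors. The documents do not support that; they support only that it could.

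A third reply is that rounding before comparison makes the rule stricter. That is correct. A reader might infer that rounding adds to the false positives, but it cannot. The McNemar examples also depend on the version of the test, which 16.1 does not specify. With continuity correction, 15 v 6 and 18 v 8 give p of about 0.081 and 0.078, non-significant either way.

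**Conclusion.** The concern holds in a limited form. One unadjusted rule governs an unstated number of quantitative and radiomic tests, and the planned feature selection is not error control. Chance features could be declared significant predictors of csPCa. The size is 0.05 per null parameter tested, so about one false positive on average at 20 null parameters and 15 at 300. These counts rest on assumed k and on those parameters being truly unrelated to csPCa; the at-least-one probabilities also assume independence.

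A reader might infer that the trial's main conclusions are at risk. They are not: the multiplicity gap leaves the primary accuracy estimates, the McNemar comparison and N=167 untouched. The rounding conflict with the 95% interval is real but very narrow and conservative, and is a wording matter only.

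**What to change.** In section 16.1:

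- Keep the unadjusted two-sided 0.05 level for the McNemar comparison.
- For the quantitative and radiomic parameters, apply Benjamini-Hochberg at a 5% false discovery rate to the tests of all candidate parameters, image sets and thresholds, counted before any selection that uses csPCa status. Applied only to the features that survive such selection, the procedure would not control the rate.
- Report how many candidates were tested.
- Describe any p-value computed after selection as exploratory.
- Compare the unrounded p-value with 0.05, and round only for display.

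The cost is a few sentences in 16.1, a fixed list of candidates, and one test per candidate before selection. Sample size, data collection and patient procedures do not change. The downside is that fewer individual features will be flagged.
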